#### **Events Meeting the AE Definition**

- Any abnormal laboratory test results (hematology, clinical chemistry, or urinalysis) or other safety assessments (e.g., ECG, radiological scans, vital signs measurements), including those that worsen from baseline, considered clinically significant in the medical and scientific judgment of the investigator (i.e., not related to progression of underlying disease).
- Exacerbation of a chronic or intermittent pre-existing condition including either an increase in frequency and/or intensity of the condition.
- New conditions detected or diagnosed after study intervention administration even though it may have been present before the start of the study.
- Signs, symptoms, or the clinical sequelae of a suspected intervention-intervention interaction.
- Signs, symptoms, or the clinical sequelae of a suspected overdose of either study intervention or a concomitant medication. Overdose per se will not be reported as an AE/SAE unless it is an intentional overdose taken with possible suicidal/self-harming intent. Such overdoses should be reported regardless of sequelae.
- Sign, symptoms, or the clinical sequelae of suspected medication errors, misuse and abuse of either study intervention or a concomitant medication. Medication errors, misuse and abuse per se will not be reported as an AE/SAE, unless it is resulting in AE/SAE. Such medication errors, misuse and abuse should be reported regardless of sequelae.
- "Lack of efficacy" or "failure of expected pharmacological action" per se will not be reported as an AE or SAE. Such instances will be captured in the efficacy assessments. However, the signs, symptoms, and/or clinical sequelae resulting from lack of efficacy will be reported as AE or SAE if they fulfill the definition of an AE or SAE.

10 MAY 2023 Page: 74 of 97

## **Events NOT Meeting the AE Definition**

- Any clinically significant abnormal laboratory findings or other abnormal safety assessments which are associated with the underlying disease, unless judged by the investigator to be more severe than expected for the participant's condition.
- The disease/disorder being studied or expected progression, signs, or symptoms of the disease/disorder being studied, unless more severe than expected for the participant's condition.
- Medical or surgical procedure (e.g., endoscopy, appendectomy): the condition that leads to the procedure is the AE.
- Situations in which an untoward medical occurrence did not occur (social and/or convenience admission to a hospital).
- Anticipated day-to-day fluctuations of pre-existing disease(s) or condition(s) present or detected at the start of the study that do not worsen.

#### **10.3.2 Definition of SAE**

## An SAE is defined as any AE that, at any dose:

#### a. Results in death

#### b. Is life-threatening

• The term 'life-threatening' in the definition of 'serious' refers to an event in which the participant was at risk of death at the time of the event. It does not refer to an event, which hypothetically might have caused death, if it were more severe.

# c. Requires inpatient hospitalization or prolongation of existing hospitalization

- In general, hospitalization signifies that the participant has been admitted (usually involving at least an overnight stay) at the hospital or emergency ward for observation and/or treatment that would not have been appropriate in the physician's office or outpatient setting. Complications that occur during hospitalization are AEs. If a complication prolongs hospitalization or fulfills any other serious criteria, the event is serious. When in doubt as to whether "hospitalization" occurred or was necessary, the AE should be considered serious.
- Hospitalization for elective treatment of a pre-existing condition that did not worsen from baseline is not considered an AE.

10 MAY 2023 Page: 75 of 97

## d. Results in persistent or significant disability/incapacity

- The term disability means a substantial disruption of a person's ability to conduct normal life functions.
- This definition is not intended to include experiences of relatively minor medical significance such as uncomplicated headache, nausea, vomiting, diarrhea, influenza, and accidental trauma (e.g., sprained ankle) which may interfere with or prevent everyday life functions but do not constitute a substantial disruption.

#### e. Is a congenital anomaly/birth defect

#### f. Other situations:

- Medical or scientific judgment should be exercised by the investigator in deciding whether SAE reporting is appropriate in other situations such as significant medical events that may jeopardize the participant or may require medical or surgical intervention to prevent one of the other outcomes listed in the above definition. These events should usually be considered serious.
- Examples of such events include invasive or malignant cancers, intensive treatment for allergic bronchospasm, blood dyscrasias, convulsions, or development of intervention dependency or intervention abuse.

## 10.3.3 Recording and Follow-Up of AE and/or SAE

#### AE and SAE Recording

- When an AE/SAE occurs, it is the responsibility of the investigator to review all documentation (e.g., hospital progress notes, laboratory reports, and diagnostics reports) related to the event.
- The investigator will then record all relevant AE/SAE information.
- It is not acceptable for the investigator to send photocopies of the participant's medical records to the sponsor in lieu of completion of the AE/SAE eCRF page.
  - There may be instances when copies of medical records for certain cases are requested by the sponsor. In this case, all participant identifiers, with the exception of the participant number, will be redacted on the copies of the medical records before submission to sponsor.
  - The investigator will attempt to establish a diagnosis of the event based on signs, symptoms, and/or other clinical information. Whenever possible, the diagnosis (not the individual signs/symptoms) will be documented as the AE/SAE.

10 MAY 2023 Page: 76 of 97

#### **Assessment of Intensity**

- The investigator will make an assessment of intensity for each AE and SAE reported during the study and assign it to 1 of the following categories:
  - Mild: An event that is easily tolerated by the participant, causing minimal discomfort and not interfering with everyday activities.
  - Moderate: An event that causes sufficient discomfort to interfere with normal everyday activities.
  - Severe: An event that prevents normal everyday activities. An AE that is
    assessed as severe should not be confused with an SAE. Severe is a category
    utilized for rating the intensity of an event; and both AEs and SAEs can be
    assessed as severe.

An event is defined as 'serious' when it meets at least 1 of the predefined outcomes as described in the definition of an SAE, NOT when it is rated as severe.

## **Assessment of Causality**

- The investigator is obligated to assess the relationship between study intervention and each occurrence of each AE/SAE.
- A "reasonable possibility" of a relationship conveys that there are facts, evidence, and/or arguments to suggest a causal relationship, rather than a relationship cannot be ruled out.
- The investigator will use clinical judgment to determine the relationship.
- Alternative causes, such as underlying disease(s), concomitant therapy, and other risk factors, as well as the temporal relationship of the event to study intervention administration will be considered and investigated.
- The investigator will also consult the Investigator's Brochure (IB) and/or Product Information, for marketed products, in his/her assessment.
- For each AE/SAE, the investigator **must** document in the medical notes that he/she has reviewed the AE/SAE and has provided an assessment of causality.
- There may be situations in which an SAE has occurred and the
  investigator has minimal information to include in the initial report to
  sponsor. However, it is very important that the investigator always
  make an assessment of causality for every event before the initial
  transmission of the SAE data to sponsor.
- The investigator may change his/her opinion of causality in light of follow-up information and send an SAE follow-up report with the updated causality assessment.
- The causality assessment is one of the criteria used when determining regulatory reporting requirements.

10 MAY 2023 Page: 77 of 97

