#### Follow-up of AEs and SAEs

- The investigator is obligated to perform or arrange for the conduct of supplemental measurements and/or evaluations as medically indicated or as requested by sponsor to elucidate the nature and/or causality of the AE or SAE as fully as possible. This may include additional laboratory tests or investigations, histopathological examinations, or consultation with other health care professionals.
- If a participant dies during participation in the study or during a recognized follow-up period, the investigator will provide sponsor with a copy of any post-mortem findings including histopathology.
- New or updated information will be recorded in the originally submitted documents.
- The investigator will submit any updated SAE data to the sponsor within 24 hours of receipt of the information.

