4.5.2. Adverse Events

Adverse events (AEs) will be collected from the start of study intervention until the last follow-up. (Serious) Adverse event ((S)AEs) which are related to protocol required study procedures (e.g. (S)AE related to invasive study procedures) will be recorded as (S)AEs from the signing of the Informed consent form (ICF) (pre-treatment (S)AEs). Any medical occurrences/conditions that begin in the period between signing ICF and the start of study intervention, and which are not related to a protocol-required study procedure, will be recorded on the Medical History/Current Medical Conditions, not as AEs.

All AEs will be summarized using the Medical Dictionary for Regulatory Activities (MedDRA) preferred terms (PT) grouped by system organ class (SOC) (the current version at the time of analysis) and classified into pre-treatment AEs, treatment-emergent (TEAE) and post-treatment AEs. Pre-treatment and post-treatment AEs will be shown by treatment group. Descriptive analysis for TEAEs will be performed for Week 1-12, 13-26, 27-52 and overall week 1-26, 27-52 and 1-52 by study drug.

Incidences of TEAEs and TESAEs per 100 person-years will be summarized by study drug and by study period (weeks 1-12, 13-26, 27-52 and overall elinzanetant for weeks 1-26 and 1-52).

The rate per 100 person-years is calculated as

Rate per 100 person-years = number of subjects with an event / (total drug exposure in years / 100),

where 365.25 days are taken as one year.

A TEAE is defined as any adverse event occurring or worsening on or after the date of the first dose of study drug up to 14 days after the date of the last dose of study drug. AEs will be flagged as TEAE except for AEs for which there is clear evidence that the AE starts before date of first study drug intake (pre-treatment AEs) or after the date of last study drug intake + 14 days (post-treatment AEs).

If the severity of a previously reported event worsens or if the relationship to study intervention/protocol required procedures changes, two separate events should be reported.

Worsening of an AE is defined as follows:

- AE intensity is worsened (e.g. moderate to severe)
- AE changed to a serious event
- AE ends with death

In case an AE starts before the date of last study drug intake + 14 days and worsens after last study drug intake +14 days, it will be considered as two AEs, a TEAE and a post-treatment AE.

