Partially missing onset AE date will be imputed following a worst-case approach as described in Section 4.1.1.

version 3.0 Page: 51 of 87

In case of events with different intensity within a subject, the maximum reported intensity will be used. If the same event is considered as both unrelated and related to the study drug within a subject, the event will be reported as related to study drug. If the drug relationship is missing, the event will be considered as being related to the study drug.

The tabulation will follow in principle the Bayer Global Standard Tables catalogue (v4.0 or later). SAEs and Adverse events of special interest (AESI) will be summarized in the same way as described for TEAEs. A separate table summarizing TEAEs that occurred in more than 5% of the subjects will be provided.

In addition, subjects with a COVID-19 as an adverse event will be listed.

Adverse events of special interest (AESI)

AESI will only be identified by Standardized MedDRA Query (SMQ) searches and PTs and AESI 'any condition triggering close liver observation' also via eCRF as further detailed in Section 6.6. The following AEs are included:

- 1. Any condition triggering close liver observation (as listed in Protocol section 10.5)
- 2. Somnolence or fatigue
- 3. Phototoxicity
- 4. Post-menopausal uterine bleeding (women without hysterectomy are considered)

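### A causality opinion revised from related to unrelated updates the report under Protocol 10.3.3, but under SAP 4.5.2 it makes a second event and the episode still counts as drug-related

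*Protocol*

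**What the plan says.** Protocol Section 8.3 points to Section 10.3 for how adverse events are recorded and how causality is assessed. Under Assessment of Causality in 10.3.3, the investigator must give a causality judgement before the first SAE transmission, even when little is known. The text then provides for correction: "The investigator may change his/her opinion of causality in light of follow-up information". For a serious event, the change is passed to the sponsor in a further SAE report. Under Follow-up of AEs and SAEs, the same section states: "New or updated information will be recorded in the originally submitted documents". Together these describe one event whose causality field is brought up to date.

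SAP Section 4.5.2 has two rules that bear on the same situation:

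- The recording rule covers worsening severity of a reported event and continues: "or if the relationship to study intervention/protocol required procedures changes, two separate events should be reported".
- The tabulation rule settles conflicting judgements: "considered as both unrelated and related to the study drug within a subject, the event will be reported as related to study drug".

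A companion rule handles gaps: "If the drug relationship is missing, the event will be considered as being related to the study drug". The SAP does not say that the last assessment prevails or that a superseded record is set aside. SAP Sections 1 and 4.8 declare no departure from the analyses planned in the protocol.

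**The concern.** Each SAP rule is defensible alone. Combined, they treat a withdrawn opinion on one episode as if it were a second, different episode. The case affected is the one that the protocol foresees: an early judgement on thin information, later corrected. If the correction becomes a new record and the old one stays, the either-record rule restores the judgement that the investigator has withdrawn.

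At stake is whether the drug-related TEAE and SAE tables show the investigators' final judgements. As the documents stand, the answer depends on whether a site or programmer follows the protocol or the SAP.

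**Working it through.** No figure in the plan is at issue, so the check sets the rules side by side.

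**Inputs.** Protocol 10.3.3: update the original report, so the last assessment stands. SAP 4.5.2: a change of relationship gives two records, and the event is related if either record is. SAP 4.5.2, rate formula: the numerator is participants with an event. Protocol 9.4.5: all safety analyses are descriptive.

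**Result by sequence of assessments for one episode, with both records in the database under the SAP:**

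| Sequence | Protocol (last) | SAP (related if either) | Differ? |
|---|---|---|---|
| Related throughout | related | related | no |
| Unrelated throughout | unrelated | unrelated | no |
| Unrelated, then related | related | related | no |
| Related, then unrelated | unrelated | related | yes |

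In general, the protocol takes the last assessment and the SAP takes the most drug-related one. They differ only when the last assessment is unrelated and an earlier one was related. The SAP then always gives the higher attribution.

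**Effect on counts of participants.** Let R be the number of participants with at least one drug-related TEAE when the last assessment is used. Let D be the number whose related judgements were all later revised to unrelated. Then:

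- Count under the SAP rule = R + D.
- Excess = D, which is zero or positive.

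A woman with a revised event and some other event that remains related is already in R and adds nothing. The same argument applies to drug-related SAEs.

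**Effect on records.** Any change of relationship, in either direction, gives two records for one episode under the SAP and one under the protocol. Listings therefore show the episode twice.

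**What does not move.** The number of participants with any TEAE is unchanged, because a second record for the same episode adds no participant. The confirmatory efficacy tests do not use these data.

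**Size.** D depends on how often causality is revised downward and in whom. Neither document gives a rate, so D cannot be calculated.

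**The case against.** The strongest reply is that the SAP analyses records and does not create them. Sites enter data under the protocol and the CRF completion guidelines mentioned in Protocol 10.1.8, which are not among the documents reviewed. If sites overwrite the causality field, only one record exists and the either-record rule has nothing to act on. This stands as a limit: the effect needs both records in the database. A reader might infer that a revision to unrelated can never take effect, and the documents do not support that unconditional claim. But if sites do overwrite, the SAP's recording rule is not being followed, and the two texts still need reconciling.

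A second reply is that the SAP means a real change in the course of an event, because it pairs relationship with worsening severity. The sentence does not say so. The SAP's own list of what counts as worsening (intensity, seriousness, death) leaves relationship out.

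A third reply is that counting as related when in doubt is a deliberate conservative convention, in line with the rules for missing relationship and maximum intensity. That is a fair defence for separate occurrences of the same term, and the rule should stay there. It is a weak reason to keep a withdrawn opinion on one episode.

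A reader might also infer that an AE which begins on placebo and worsens after the Week 12 switch stays one record and is graded to placebo. The documents do not show this. No protocol text requires a worsened AE to remain one record, and SAP 4.5.2 already calls for two events on worsening.

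**Conclusion.** The inconsistency is real and narrow. Where both records exist, an episode first judged related and finally judged unrelated is tabulated as drug-related and listed twice, contrary to the updating procedure in the protocol. The discrepancy never runs the other way.

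Its reach is limited to descriptive safety output. It can raise the number of participants with drug-related TEAEs or SAEs by D, the women with no other related event, and it adds records to the listings. The same rule applies in both arms. A reader might infer a general inflation of adverse event counts or a bias in the trial's conclusions. Neither follows, because participants are the counting unit and no hypothesis test uses these data.

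The conclusion rests on the wording of the two documents and on the condition that the superseded record is kept. No percentage can be attached to it without a revision rate, which the documents do not supply.

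**What to change.** Amend SAP 4.5.2 only:

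1. Remove the relationship trigger from the sentence ending "or if the relationship to study intervention/protocol required procedures changes, two separate events should be reported", so that the two-events rule applies to worsening alone.
2. State that a revised causality opinion updates the existing record and that the investigator's last assessment of that event is analysed.
3. Keep the related-if-either rule, limited explicitly to distinct occurrences of the same term within a participant.

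No protocol amendment is needed, because Protocol 10.3.3 already describes updating the original report. The cost is a short text change in the SAP and a check that table programming follows it. If pairs of records have already been entered for one episode because of a changed opinion, they must be linked so that the last assessment can be identified. The downside is that drug-related counts become slightly less conservative, by the D participants defined above.

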#### Follow-up of AEs and SAEs

- The investigator is obligated to perform or arrange for the conduct of supplemental measurements and/or evaluations as medically indicated or as requested by sponsor to elucidate the nature and/or causality of the AE or SAE as fully as possible. This may include additional laboratory tests or investigations, histopathological examinations, or consultation with other health care professionals.
- If a participant dies during participation in the study or during a recognized follow-up period, the investigator will provide sponsor with a copy of any post-mortem findings including histopathology.
- New or updated information will be recorded in the originally submitted documents.
- The investigator will submit any updated SAE data to the sponsor within 24 hours of receipt of the information.

#### 10.3.4 Reporting of SAEs

#### SAE Reporting to sponsor via an Electronic Data Collection Tool

- The primary mechanism for reporting an SAE to sponsor will be the electronic data collection tool.
- If the electronic system is unavailable, then the site will use the paper SAE data transmission (see next section) to report the event within 24 hours.
- The site will enter the SAE data into the electronic system as soon as it becomes available.
- After the study is completed at a given site, the electronic data collection tool will be taken off-line to prevent the entry of new data or changes to existing data.
- If a site receives a report of a new SAE from a study participant or receives updated data on a previously reported SAE after the electronic data collection tool has been taken off-line, then the site can report this information on a paper SAE form (see next section) or to the local pharmacovigilance contact person by telephone.
- Contacts for SAE reporting can be found in the investigator site file.

10 MAY 2023 Page: 78 of 97

## **SAE Reporting to Sponsor via Paper Data Collection Tool**

- Email transmission of the SAE paper data collection tool is the preferred method to transmit this information to the sponsor's Pharmacovigilance department.
- In rare circumstances and if email transmission is not feasible, notification by telephone is acceptable with a copy of the SAE data collection tool sent by overnight mail or courier service.
- Initial notification via telephone does not replace the need for the investigator to complete and sign the SAE data collection tool within the designated reporting time frames.
- Contacts for SAE reporting can be found in the Investigator Site File.

## **10.4** Appendix 4: Collection of Pregnancy Information

## 10.4.1 Definitions

## Woman of Childbearing Potential (WOCBP)

A woman is considered fertile following menarche and until becoming post-menopausal unless permanently sterile (see below).

Women in the following categories are considered WOCBP (fertile)

- 1. Following menarche
- 2. From the time of menarche until becoming postmenopausal unless permanently sterile (see below).

A postmenopausal state is defined as:

- $\geq$ 12 months of spontaneous amenorrhea in the absence of other physiological or pathological causes (e.g. pregnancy, thyroid disease, hyperprolactinemia) or
- Surgical menopause as a result of bilateral oophorectomy with or without hysterectomy at least 6 weeks prior to signing of informed consent

Permanent sterilization methods (for the purpose of this study) include:

- Documented hysterectomy
- Documented bilateral salpingectomy
- For individuals with permanent infertility due to an alternate medical cause other than the above, (e.g., Mullerian agenesis, androgen insensitivity, gonadal dysgenesis), investigator discretion should be applied to determining study entry.

**Note**: Documentation can come from the site personnel's: review of the participant's medical records, medical examination, or medical history interview.

If fertility is unclear (e.g., amenorrhea in athletes, post-chemotherapy amenorrhea) and a menstrual cycle cannot be confirmed before first dose of study intervention, additional evaluation should be considered.

10 MAY 2023 Page: 79 of 97

Women in the following categories are considered WONCBP:

- 1. Pre-menopausal female with permanent infertility due to one of the following:
  - Documented hysterectomy
  - Documented bilateral salpingectomy
  - Documented bilateral oophorectomy
  - For individuals with permanent infertility due to an alternate medical cause other than the above, (e.g., Mullerian agenesis, androgen insensitivity, gonadal dysgenesis), investigator discretion should be applied to determining study entry.
- 2. Postmenopausal women (see definition above)

**Note**: Documentation can come from the site personnel's review of the participant's medical records, medical examination, or medical history interview

